4.8 Data analysis

Because the number of features is much higher than the data set, it will be necessary to reduce their number using feature selection and extraction techniques that allow choosing those characteristics that have greater discriminating power.

A predictive model of survival will then be elaborated based on the selected features. The performance evaluation strategy of the predictive survival model will be adjusted to the sample size. The options to be tested will be five and ten-fold cross-validation, the random split of the sample into a training cohort and testing cohort (unseen data), and an external validation cohort formed by one of the collaborating centers.

5. Team and Scientific Potential:

The research group that we have assembled has already collaborated in the past and has carried out various tasks focused on integrating non-invasive diagnostic tools for neurological pathologies and creating new imaging methods applicable to neurosurgical patients.

The principal investigator ([name]) is currently collaborating with an international network dedicated to the study and advanced analysis of images in glioblastomas, ReSPOND (Radiomics Signatures for PrecisiON Diagnostics) consortium on glioblastoma (GBM).

At the national level, [name] collaborates with the recently established National Brain Metastasis Network (RENACER), a project promoted by the National Center for Oncological Research. Our center has also collaborated for several years with the National Registry of Central Nervous System Tumors (RETSINE) of the Spanish Research Group in Neuro-Oncology.

Since 2019, the IP is the Coordinator of the Central Nervous System Tumors Committee of the Río Hortega University Hospital.

Our team has collaborated with the Image Processing Laboratory (IPL) of the Higher Technical School of Telecommunications Engineering (HTST) of the University of Valladolid (www.lpi.tel.uva.es), which has been studying diagnostic image processing for years, performing multiple projects and having high-level expertise in this field.

The project will have the collaboration of the following international centers:

1. [name] [name] (Fondazione Policlinico A. Gemelli, IRCSS, Rome, Italy)
2. [name] [name] (Tata Memorial Center, Mumbai, India)
3. [name] [name] (Fondazione Istituto Neurologico Carlo Besta, Milano, Italy)
4. [name] (Philipps University of Marburg, Marburg, Germany)
5. [name] (CHRU de Tours and Inserm U1253, Tours, France).

Our working group has previously published several articles about applying ioUS and advanced analysis of MRI. Our original works constitute the first descriptions in the literature about the semi-quantitative analysis of strain-type elastography in brain tumors and peritumoral regions, predicting tumor consistency in meningiomas combining radiomic features of MRI and ioUS elastography. Similarly, we are the first research group to describe the use of artificial intelligence techniques (Machine and Deep Learning) and radiomic analysis of intraoperative ultrasound images of brain tumors.

6. Ethics:

The data will originate from measurements, comparisons and validations. They will be used to meet project objectives and in peer-reviewed conferences and publications. The types of data generated in the investigation will be of type:

- Observational: data captured in real-time (neuroimaging)
- Simulation: data generated from test models (mathematical)
- Compiled: data mining, compiled databases, etc.
- Reference: clustered data sets (radiomic neuroimaging measurements).

Most of the data will be in ASCII (American Standard Code for Information Interchange) data files, for example, Comma Separated Variables (CSV) format, which can be imported into rich text files for word processing or into spreadsheets. If specialized software is used, information on free readers will be provided. Neuroimaging data will be collected in Digital Imaging and Communication On Medicine (DICOM) format.

All data associated with scientific publications will be openly available by default unless there is a specific reason for not publishing the data. There will be no restrictions on the use of published data, but users should acknowledge the study group and the data source in any resulting publication. The research team members will impose a strict policy on all employees, co-workers, subcontractors, etc., who have access to the data. This policy will include but is not limited to, not allowing copies on local devices during data processing.

The transfer of data about human beings to the repository will only be considered when: informed consents, ethical approval and, where applicable, approval of local data protection authorities cover the purpose for which the data is intended to be used. Since this study involves patients diagnosed with glioblastomas, the cases have perished at the time of data collection. Therefore, the exemption of informed consent will be requested for the retrospective phase of the study (see Annex). On the contrary, for the prospective collection of cases, the informed consent model will be used (see Annex). All data to be transferred to the repository will be pseudonymized. The data owner/data provider will be responsible for the pseudonymization process and ensure that identifiable variables are not transferred to the repository.

7. Communication Plan for Dissemination:

This project's results will be disseminated through its publication in scientific journals and international conferences focused on neuroimaging, ultrasound, neurosurgery, and neuro-oncology.

8. Outputs: Impact, potential beneficiaries and added value:

The research work, aligned with one of the items of the Horizon 2020 program (Health, Demographic Change and Wellbeing) in addition to two of the United Nations Sustainable Development Goals (Health and well-being, 3; Industry, Innovation and Infrastructure, 9), has a great potential for impact, both at a scientific-technical level and a socio-economic level.

Concerning the scientific-technical, it is considered that the development of models for pre-processing, advanced analysis of ultrasound images that apply to commercial scanners and that, in turn, derive in descriptors that generate a large amount of useful information about the macro and microstructural properties of brain tumors, will lead to an increase in the use of advanced ultrasound techniques in clinical practice and will generate an increase in scientific research projects focused on these imaging technique. Furthermore, such models' implementation will substantially improve radiological care (diagnosis, early detection and treatment).

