3.2 Hypotheses

Intraoperative ultrasound images in B-mode harbour tumor texture features correlated with overall survival in glioblastomas.

3.4 Objectives:

- To determine the relationship between the radiomic features of intraoperative ultrasound B-mode and overall survival in glioblastomas.
- Develop a predictive survival model using the texture features with the highest discriminatory power.
- Validate the model against an external dataset and compare it with currently available predictive models.
- Build a data set that allows exploring various image harmonization techniques that allow the reproducibility of our predictions.
- Establish an international cooperation network (**BraTioUS-DB**) whose objective will be to interchange ultrasound images and clinical data of patients operated on for a brain tumor prospectively from its creation and start-up.

4. Research Plan:

4.1 Study sample:

The cases that meet the inclusion criteria mentioned in the following section will be collected retrospectively to carry out the project's first phase. From January 2018 to January 2020, it is

estimated that each center can contribute with a minimum of 20 cases. Therefore, the total sample size for this phase of the study will be approximately 120 patients.

4.2 Selection of patients:

The inclusion criteria will be:

- Adult patients operated between January 2018 and January 2020 with a pathological diagnosis of WHO grade IV astrocytoma (Glioblastoma).
- Intraoperative ultrasound study that includes B-mode images

The exclusion criteria will be:

- Other histopathological diagnoses. Even though the international database will be established in such a way that other tumor types can be included prospectively.
- Artifacts in ultrasound images that make their analysis impossible
- Stereotactic biopsies.

4.3 Data collection (retrospective phase):

Each center will collect the details of the intraoperative acquisition technique of the ultrasound images. These data should include:

- Manufacturer of the ultrasound equipment,
- Type of probe: linear, curve.
- Footprint size
- Frequency range
- Modality. Essential B-mode, other modes optional.
- Acquisition before or after dural opening.
- Co-registered magnetic resonance images when possible (navigated ultrasound).
- Number of explorers who perform the ultrasound study.

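### Section 4.8 keeps a random training/testing split as an option although, at about 120 patients, more than half of the variance of its C-index comes from the draw

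*Protocol*

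**What the plan says.** Section 4.8 leaves the evaluation method open: "The performance evaluation strategy of the predictive survival model will be adjusted to the sample size". It then names the candidates. "The options to be tested will be five and ten-fold cross-validation" comes first, followed by "the random split of the sample into a training cohort and testing cohort (unseen data", and finally "an external validation cohort formed by one of the collaborating centers". No split ratio, number of splits or number of cross-validation repeats is given.

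Section 4.1 states that "the total sample size for this phase of the study will be approximately 120 patients", because it is "estimated that each center can contribute with a minimum of 20 cases". Section 4.8 also says that "the number of features is much higher than the data set", so the model depends on heavy feature selection.

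**The concern.** A random split uses each patient once, either to build the model or to test it. With about 120 patients the test cohort is small, so the C-index can move a good deal when the same patients are split with another seed. If that figure were reported as the model's performance (the second objective in the protocol's list), a weak model could look useful or useless on identical data. Cross-validation tests every patient, and averaging over repeated partitions removes most of the seed dependence without any new data. The expected size is already in the protocol, so the suitability of a split can be judged now.

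**Working it through.** **1. The plan's own figure.** Section 5 introduces the partners with "The project will have the collaboration of the following international centers" and lists five. With the host hospital that makes 6 centres, and 6 x 20 = 120, which matches Section 4.1. Five centres would give 5 x 20 = 100, which does not. The figure is a feasibility count.

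**2. Size of the cohorts.** The ratio is not stated, so 80/20 and 70/30 are assumed.
- 80/20: test 0.2 x 120 = 24, training 96.
- 70/30: test 0.3 x 120 = 36, training 84.
- Five-fold: training 96 in each fold; ten-fold: 108. In both, all 120 patients are tested.

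**3. Main simulation.** 120 patients; all deaths observed (Section 6 treats the retrospective cases as deceased); exponential proportional-hazards survival; 100 or 500 correlated features (the protocol gives no number). The five best univariate features and a ridge model were refitted inside every training set. There were 150 data sets with 40 partitions per method, in four scenarios with true mean C of 0.501, 0.555, 0.649 and 0.665. Partition share = (partition SD)² / [(partition SD)² + (between-data-set SD)²].

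| Scheme, run once | Partition SD of C | Partition share of variance | 5th-95th percentile range on one data set | RMSE against true C |
|---|---|---|---|---|
| 80/20 split | 0.063-0.064 | 62-72% | 0.190-0.195 | 0.075-0.078 |
| 70/30 split | 0.050-0.053 | 55-69% | 0.152-0.160 | 0.061-0.075 |
| Five-fold | 0.021-0.027 | 19-31% | 0.062-0.083 | 0.047-0.052 |
| Ten-fold | 0.020-0.027 | 16-21% | 0.060-0.084 | 0.044-0.060 |

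Five-fold cross-validation averaged over 40 repeats had an RMSE of 0.040-0.046.

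**4. Second simulation, other assumptions.** 120 patients, 80-89% deaths, 200 correlated features, selection and penalised Cox refitted in each training set. Partition SD was 0.051 (70/30), 0.065 (80/20) and 0.024 (one five-fold pass). In one fixed data set with true mean C of about 0.56, 95% of 70/30 splits gave C between 0.46 and 0.65, and 95% of 80/20 splits between 0.43 and 0.68.

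The variance relative to fully repeated cross-validation is (s² + p²)/s², where s is the patient-sampling SD and p the partition SD. It depends on s:
- s = 0.035: 70/30 (0.001225 + 0.002601)/0.001225 = 3.1; 80/20 (0.001225 + 0.004225)/0.001225 = 4.4; five-fold (0.001225 + 0.000576)/0.001225 = 1.5.
- s = 0.045: 70/30 (0.002025 + 0.002601)/0.002025 = 2.3; 80/20 (0.002025 + 0.004225)/0.002025 = 3.1; five-fold (0.002025 + 0.000576)/0.002025 = 1.3.

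The five-fold partition share at s = 0.035 is 0.000576/0.001801 = 32%, the upper end of the range for cross-validation.

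**5. Cost of the smaller training set.** With a moderate signal and 500 features (true mean C 0.649), mean estimated C was 0.616 for 70/30, 0.629 for 80/20, 0.630 for five-fold and 0.640 for ten-fold.

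**6. Effect of repetition.** Residual partition SD is p/√R. For five-fold with p = 0.027: 0.027/√10 = 0.0085 and 0.027/√50 = 0.0038. The sampling SD is unchanged.

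**7. The external centre.** With 100 patients for training and 20 for testing, the SD of C was about 0.08.

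**The case against.** The split is one option beside cross-validation and an external centre, and the strategy is to follow the sample size, so the sponsor can still drop it. This stands, and it limits the weight of the point. It does not remove it, because the expected size is stated and the split is still listed. Twenty per centre is an estimated minimum, so the final number could be larger; larger samples were not simulated.

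Three stronger readings are tempting, and the protocol supports none of them.
- A reader might infer that cross-validation here is also mostly luck because it is run once. The text gives fold counts only and is silent on repeats, a detail commonly left to an analysis plan. Even for one pass, the partition is the smaller part of the variance.
- A reader might infer that the label of unseen data is false because cross-validation will already have used the test patients. The protocol does not say this; cross-validation inside the training cohort, with the test cohort held back, is an equally open reading.
- A reader might infer that external validation (the third objective) is undermined. That objective calls for an external dataset, and Section 4.8 offers an external centre for it.

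It is also fair to object that the held-out centre is itself imprecise: its SD of about 0.08 is no better than the total SD of a single split (0.061-0.081). It still answers a question that no random split can, namely performance in another centre, but the imprecision has to be disclosed.

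**Conclusion.** The point holds for the random split, as a cheap improvement to a listed option and not as an error in a committed analysis. At about 120 patients, a single split with 24-36 test patients gives a C-index whose variance comes mostly from the draw (55-72% in the main simulation; partition SD about 0.05-0.065 across both). For five- or ten-fold cross-validation the partition share is about 16-32%. Repetition there lowers the RMSE of five-fold only from 0.047-0.052 to 0.040-0.046.

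The exact shares rest on the assumed split ratio, number of features, signal strength and model. The ordering did not change in any scenario: more than half for the split, less than one third for cross-validation. The variance multiples are less stable: about 2.3-3.1 for 70/30 and 3.1-4.4 for 80/20 as the sampling SD goes from 0.045 to 0.035. Most of the uncertainty left after repetition is the size of the sample itself.

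**What to change.** In Section 4.8:
- Delete the random-split option.
- State that internal performance comes from K-fold cross-validation repeated with pre-set seeds, for example 50 or more times.
- State that feature selection and tuning are refitted inside every training fold. Repetition cannot repair selection done once on all patients: with no signal and 500 features, that gave a mean C of 0.645 against a true 0.50.
- Report the mean C-index with an interval that reflects patient sampling, such as a bootstrap over patients. The spread across repeats is not a confidence interval.
- Reserve the term unseen data for the held-out centre, and report that centre with its own interval.

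The cost is computing time and a few sentences; no new patients or data are needed. The downsides are that there is no simple two-cohort figure to show, and that the external estimate from about 20 patients stays imprecise (SD of C about 0.08). The sampling SD of about 0.035-0.05 also remains.

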In recent publications, we have explored intraoperative ultrasound's ability to differentiate primary malignant tumors from metastases using artificial intelligence. Besides, we have made the first descriptions about the extraction of brain tumors' ultrasound radiomic characteristics and their correlation with survival. The ultrasound's main limitation is the dependency on the

explorer and the variability between the parameters used in image acquisition among different centers. For this reason, image pre-processing is a fundamental step. In this project, we intend to use an ultrasound modality as a reference, the B-mode. Only by gathering a vast set of cases we would be able to test image harmonization techniques to allow the generalization and adoption of our predictive model in other centers. Also, the creation of an international and public database, the **Brain Tumor intraoperative UltraSound DataBase (BraTioUS-DB)**, will allow the development of additional research lines, since, in addition to B-mode images, other modalities such as elastography, CEUS, vascular studies, etc. will be incorporated prospectively. Furthermore, other histopathological tumor types could also be included.

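### Section 3.4 promises external validation, but section 4.8 does not firmly commit to it, and the one-centre cohort it offers, about 20 patients, would give an imprecise result

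*Protocol*

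**What the plan says.** - **Section 3.4 (Objectives)** lists, without condition: "Validate the model against an external dataset and compare it with currently available predictive models".
- **Section 4.8 (Data analysis)** states: "The performance evaluation strategy of the predictive survival model will be adjusted to the sample size". It continues: "The options to be tested will be five and ten-fold cross-validation, the random split of the sample" into training and testing cohorts, and ends the list with "an external validation cohort formed by one of the collaborating centers". It does not say which centre this would be, how large it must be, or under what condition the option is used. It does not say that the folds or the random split keep centres apart.
- **Section 3.1 (Background)** names, as part of the main limitation of ultrasound, the "variability between the parameters used in image acquisition among different centers".
- **Section 4.1 (Study sample)** gives the size. It is "estimated that each center can contribute with a minimum of 20 cases", and "the total sample size for this phase of the study will be approximately 120 patients".
- **Section 5 (Team)** says "The project will have the collaboration of the following international centers" and lists five. With the host hospital that makes six.

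**The concern.** There are two linked problems.

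First, an unconditional objective in 3.4 becomes, in 4.8, one item in a list whose use depends on sample size. If only the cross-validation or the random split is run, patients from the same centre can fall in both training and test data. The objective is then not met, and transfer to a centre with different equipment and settings, which the protocol itself treats as a main difficulty, is not tested.

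Second, if the one-centre cohort is used, it is small. A discrimination estimate from about 20 patients may be too imprecise to show that a model of modest performance carries over. A single centre also cannot show how performance differs between centres.

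**Working it through.** **1. Size of the held-out centre.** Five listed centres plus the host, each with the minimum of 20: (5 + 1) × 20 = 120, which reproduces the total in 4.1. Five centres alone would give 5 × 20 = 100, which does not. One held-out centre is therefore about 20 patients, leaving about 120 − 20 = 100 for development. Since 20 is an estimated minimum, 30 and 40 were also tried.

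**2. Assumptions.** The protocol names no performance measure, so the C-index (the share of comparable patient pairs that the score ranks correctly) and its true values are assumptions. All patients are taken as dead, as section 6 states, which is the most favourable case. Survival is exponential with proportional hazards and a standard normal risk score. For log hazard ratio b per SD, the true C is the mean of 1/(1 + exp(−b·|d|)), where d is the difference between two patients' scores, with variance 2. Values of b of 0.370, 0.539, 0.734 and 1.032 give C = 0.60, 0.64, 0.68 and 0.73.

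**3. One centre of 20, score treated as fixed** (40,000 simulated samples; half-width = 1.96 × SD; range = 2.5% to 97.5% quantiles):

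| True C | SD | Half-width | Range |
|---|---|---|---|
| 0.60 | 0.078 | 0.15 | 0.44 to 0.74 |
| 0.64 | 0.075 | 0.15 | 0.48 to 0.78 |
| 0.68 | 0.072 | 0.14 | 0.53 to 0.81 |
| 0.73 | 0.066 | 0.13 | 0.59 to 0.85 |

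A score with no discrimination (C = 0.50) ranges over 0.34 to 0.66 at this size, so an observed 0.64 would be compatible with a useless model.

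**4. A larger centre, true C 0.64.** With 30 patients: 1.96 × 0.060 = 0.12, range 0.52 to 0.75. With 40: 1.96 × 0.051 = 0.10, range 0.54 to 0.73.

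**5. Some patients still alive.** Censoring at 21 to 50 months, derived from the surgery window and study dates, leaves about 14 to 16 events in 20 patients. The half-widths become 0.16, 0.15, 0.15 and 0.14 at true C 0.60, 0.65, 0.70 and 0.75. The conclusion does not rest on everyone having died.

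**6. Alternative: each centre left out in turn, within-centre C pooled over 6 × 20.**

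| Scenario | One centre of 20 | Pooled over six |
|---|---|---|
| Fixed score, C 0.64 | 0.48 to 0.78 (SD 0.075) | 0.58 to 0.70 (SD 0.031) |
| Selection and fitting repeated in each training set of 100, mean C 0.64 | 0.48 to 0.78 (SD 0.077) | 0.56 to 0.71 (SD 0.035) |
| Fixed score, effect varying between centres (log-HR mean 0.55, SD 0.3) | 0.42 to 0.81 (SD 0.099) | 0.55 to 0.71 (SD 0.041) |

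The second row (1,500 samples) assumes 100 correlated features loading on ten factors, two of them prognostic with log-HR 0.55 each, five features selected by univariate Cox models, and a ridge Cox fit. Half-widths there are 1.96 × 0.077 = 0.15 and 1.96 × 0.035 = 0.07. With a weaker signal (log-HR 0.45, mean C 0.62) the SDs are 0.081 and 0.039.

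**The case against.** The strongest reply is that 4.8 speaks of options to be tested and joins them with an and. The natural reading may be that all are run, in which case the external cohort is evaluated and 3.4 is served. That reading is possible, so the point is only that the commitment is unclear; external validation is not left out. The ambiguity remains because the sentence before makes the strategy depend on sample size.

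Twenty is a minimum and the chosen centre might be larger. This stands, but 40 patients still give a half-width of 0.10 at C 0.64. It also stands that the ranges at 20 patients exclude 0.5 once the true C reaches 0.68, so the inability to tell the model from chance is confined to modest discrimination. The half-width is nevertheless 0.13 to 0.15 at every C in the main table.

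The measure, the interval method and the ranking of validation schemes can properly be left to a statistical analysis plan. Their absence is not the complaint. What the protocol itself fixes badly is the commitment and the cohort.

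Leave-one-centre-out is no complete answer either. Its gain comes mainly from evaluating 120 patients in place of 20. It tests six related models and no frozen one, and the final model fitted on all patients has no external test. Each centre's own C remains as imprecise as before: with six centres of 20 and no true heterogeneity, the highest and lowest differ by a median of about 0.18, and power to detect a between-centre SD of 0.3 in log-HR is about 27%. These limits stand. They are reasons to word 3.4 carefully, and they do not make the single small centre more informative.

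**Conclusion.** The concern holds. Section 3.4 promises without condition what 4.8 leaves open, and the cohort offered is about 20 patients on the protocol's own figures. At that size the 95% half-width of the C-index is about 0.13 to 0.15 for true C between 0.60 and 0.73. For a model of modest discrimination the result could not show that performance carries over to another centre. Pooling over six left-out centres about halves the half-width, from 0.15 to 0.07 in the refit simulation.

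The imprecision rests on the C-index as the measure, an exponential proportional-hazards model and about 20 patients in the centre; it does not depend on which true C is assumed or on complete follow-up. The size of the gain from pooling rests further on the assumed feature structure and amount of between-centre variation. This should be corrected. It does not undermine the data collection.

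**What to change.** In 4.8, commit to an evaluation that separates centres. The preferred form is leave-one-centre-out (internal-external) validation over all six centres, with feature selection, any preprocessing that learns from the data, and model fitting repeated in each training set. Report each centre's C-index and the pooled within-centre C-index, with confidence intervals. Keep k-fold cross-validation and the random split as secondary internal validation, and fit the final model on all patients.

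In 3.4, speak of an external dataset only if a separate one is obtained. If a single held-out centre is kept instead, say plainly that this validation will be done and report its interval.

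The cost is wording in two sections and six refits on data already to be collected. There are two disadvantages: the procedure is evaluated and not one frozen model, and the headline C-index will probably be lower than from cross-validation that mixes centres.
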